7.3 Missing Data

7.3.1 General

Participants who discontinue treatment before the end of the scheduled 14 days treatment period will remain in the study and complete assessments as scheduled unless they die, start an alternate experimental treatment, or withdraw consent. Data collected at scheduled visits following discontinuation of study treatment will be included in all analyses.

Participants who are discharged from hospital before the end of the 42-day study period will be asked to complete a participant diary everyday with details of their symptoms, any AEs experienced and any changes to their concomitant medications.

Imputation rules for individual variables with missing data have been provided in [Section 5.3](#).

7.3.2 Partial Dates/Times

Partial dates and times for AEs, medical conditions and concomitant medications will be imputed for the purpose of assigning study phases and calculating duration. Listings will always include the reported date/time information rather than any imputations.

Partial AE onset and concomitant medication start dates will be imputed as follows:

- If only the month and year are specified, and the month and year of the start of treatment are not the same as the month and year of the start date, then use the 1st of the month.
- If only the month and year are specified, and the month and year of the start of treatment are the same as the month and year of the start date, then use the date of start of treatment. If this results in a start date after a known or partial end date, then use the 1st of the month.
- If only the year is specified, and the year of the start of treatment is not the same as the year of the start date, then use January 1 of the year of the start date.
- If only the year is specified, and the year of the start of treatment is the same as the year of the start date, then use the date of the start of treatment. If this results in a start date after a known or partial end date, then use January 1 of the year of the start date.
- If the start date is completely unknown, then use the date of the start of treatment. If this results in a start date after a known or partial end date, do not impute the start date.

Partial AE onset and concomitant medication start times will be imputed as follows:

- If the actual or imputed start date is the same as the treatment start date, and the start time is completely missing, then use the time of start of treatment.
- If the actual or imputed start date is not the same as the treatment start date, and the start time is completely missing, then use 00:00 h.
- If the actual or imputed start date is the same as the treatment start date, and the start time is partially missing then use the following:
 - If the hour is missing (XX:mm) then use the complete time of the start of treatment (i.e., both hours and minutes)
 - If the minutes are missing (hh:XX), use hh:59 h.
- If the actual or imputed start date is not the same as the treatment start date, and the start time is partially missing then use the following:
 - If the hour is missing (XX:mm) then use the 00:mm h
 - If the minutes are missing (hh:XX), use hh:00 h

Partial medical conditions start dates will be imputed as follows:

- If only the month and year are specified, then use the 1st day of the month.

- If only the year is specified, then use January 1st of that year.
- If the start date is completely unknown, do not impute the stop date.

Partial AE resolution, medical condition stop dates and concomitant medication stop dates and date last smoked will be imputed as follows:

- If only the month and year are specified, then use the last day of the month.
- If only the year is specified, then use December 31 of that year.
- If the stop date is completely unknown, do not impute the stop date.

Partial AE resolution and concomitant medication stop times will be imputed as follows:

- If the actual or imputed stop date is non-missing, and the stop time is completely missing, then use 23:59h on that date.
- If the actual or imputed stop date is non-missing, and the stop time is partially missing, then use 23:mm h for missing hours and hh:59 h for missing minutes.
- If the actual or imputed stop date is missing, do not impute the stop time.

7.3.3 Adverse Event Information

AEs with missing severity will be considered as 'Severe' for summary purposes but recorded as missing in the listings.

AEs with missing relationship will be considered 'Related' for summary purposes but recorded as missing in the listings.

7.4 Interim Analyses and Data Monitoring

An independent data monitoring committee (DMC), consisting of at least a chairperson, two physicians independent of the study team and an unblinded statistician will monitor the safety for the study in an ongoing fashion. DMC support staff for blinded sessions will include the Principal Investigator, the Evelo medical monitor, a blinded statistician, the Evelo Chief Medical Officer and an Evelo clinical operations representative.

7.4.1 Purpose of Interim Analyses

The purpose of the planned interim analyses will be to:

- Allow for the ongoing safety monitoring of the study.
- Provide information for the DMC recommendation on whether recruitment can be open to participants aged >65.
- Provide information for the DMC recommendation on whether recruitment should be increased to a further 40 participants.

7.4.2 Planned Schedule of Interim Analyses

Interim analyses are planned after 10, 20, 30, 40 and 60 participants have completed 7 days follow-up after their last dose (Day 21 for participants who complete dosing as scheduled).

At all interim analyses, the DMC will review safety and study disposition data to assess the safety of the interventions and to monitor the overall conduct of the study. Safety review will focus on the number and details of severe and serious adverse events, gastrointestinal (GI) events of any grade and laboratory data which meets the criteria for potentially clinically important (PCI).

At the second interim, after 20 participants have completed 7 days of follow-up after their last dose, the DMC will also specifically address the question of recruitment can be opened to participants aged >65 years.

At the final interim, after 60 participants have completed 7 days of follow-up after their last dose, the DMC will also review the efficacy data in order to make a recommendation on whether recruitment should be extended to a further 40 participants.

7.4.3 Scope of Adaptations

At all DMC meetings, the iDMC can recommend one of the following options for the study:

- The study may continue
- The study may continue with modifications (to be provided in the minutes)
- Temporary suspension of the study
- Termination of the study

Their recommendation will be based on a review of relevant unblinded safety data and where appropriate unblinded efficacy data for them to review the risk/benefit profile of EDP1815 in comparison with placebo.

At the second DMC (20 participants at Day 21) meeting, the DMC members will be asked to make additional recommendations, based on safety data, on whether the eligibility criteria should be extended to allow adults aged >65 years to enter the study.

At the final DMC (60 participants at Day 21) meeting, the DMC members will be asked to make a recommendation as to whether an additional 40 participants should be recruited into the study. There are no precise or pre-defined rules for this recommendation and DMC members will be asked to use their clinical expertise and experience. The option to extend to 100 participants should be strongly considered where there appears to be an emerging clinically meaningful treatment difference, but where the size of variation means that no significant conclusions can be drawn on efficacy. If there is clear efficacy shown, no evidence of efficacy shown or a concern regarding safety then no further recruitment should be recommended. Guidance on this decision, including some hypothetical scenarios provided for illustrative guidance to the DMC are provided in the DMC Charter.

7.4.4 Stopping Rules

The study stopping criteria, in [Section 6.6.1](#) of the protocol, specify that the study should be terminated if either of the following conditions are met:

- One (or more) participants on treatment with EDP1815 has symptoms of a clinically significant bacteremia and has a positive blood culture for the EDP1815 strain of *P. histicola*.
- The iDMC believes that EDP1815 is potentially detrimental to participant outcomes.

In addition, the DMC may recommend stopping the study for the following reasons:

- The data show a distinct increased risk of serious adverse effects in the active treatment group.
- It becomes clear that successful completion of the study is not feasible (e.g. there is an excess of participant dropout, missing data, lack of recruitment, etc.)
- Other important safety finding(s) as identified by the Sponsor or iDMC.
- The risk/benefit profile for the product is deemed to have changed and is considered unacceptable for the study to continue.

7.4.5 Practical Measures to Minimize Bias

The unblinded interim summaries and analyses will be performed by an unblinded team led by the unblinded statistician who sits on the iDMC as a non-voting member. The members of the unblinded team will not be involved in any aspects of study trial conduct, including the development of the final summaries and analyses for the study.

No unblinded data, either as individual participant results or as aggregated summaries will be shared by with any study personnel involved in the conduct or final reporting of the study.

Interim results of the analysis, beyond the recommendations to continue, modify, suspend or stop the study, will not be shared with the sponsor prior to the end of the study in order to avoid any bias or potential alpha-spending issues as per the FDA guidance on Adaptive Designs for Clinical Trials of Drugs and Biologics.

The expected summaries and listings which will be provided to the iDMC, both in blinded and unblinded form will be a subset of those expected for the final analysis and will be flagged as such in the list of tables, figures and listings in Appendix 1: List of Tables, Figures and Listings.

7.4.6 Documentation of Interim Analyses

All unblinded data and summaries together with minutes from the closed sessions will be held in a restricted file structure by the unblinded statistician until after the study has finished and the data has been unblinded after database lock.

A DMC charter is available to provide further details of the required documentation, content and structure of the iDMC meetings.

7.5 Multiple Testing

No adjustments for alpha spending will be performed.

8 Summary of Study Data

All continuous variables will be summarized using the following descriptive statistics: n (non-missing sample size), mean, SD, median, maximum and minimum. The frequency and percentages (based on the non-missing sample size) of observed levels will be reported for all categorical measures.

In general, all data will be listed, sorted by randomized treatment (Placebo, EDP1815) and participant number. If additional sites are added, then data will be sorted by participant number within site. Relevant listings will include whether the assessment was performed and the date, study day/visit and time of the assessment as applicable.

Unless otherwise specified below, all summary tables will be structured with a column for each treatment (placebo, EDP1815) and, for data collected prior to dosing, will include an overall total column where appropriate.

Columns will be ordered and labelled as follows:

- Placebo
- EDP1815
- Total

Except for disposition tables in which it is appropriate to include screened subjects, the enrolled population will be used, otherwise the ITT population will be used for all summaries of disposition, demographic and baseline data and efficacy.

The safety population will be used for all summaries of safety.

Unless otherwise specified, all listings will be produced using the ITT population.

8.1 Subject Disposition

All subject disposition summaries will be presented by treatment group and overall. The ITT population will be used unless otherwise specified.

Completion/withdrawal from the study and completion/discontinuation from treatment, together with reasons for withdrawal from the study or discontinuation from treatment will be listed and the following will also be tabulated

- Number and percentage of participants who completed the study
- Number and percentage of participants withdrawn from the study and the reported reason for withdrawal

- For the interim analyses, the number and percentage of participants still ongoing in the study will also be presented
- Number and percentage of participants who completed the 14-day treatment period
- Number and percentage of participants who discontinued treatment early and reason for discontinuation
- For the interim analyses, the number and percentage of participants who have treatment ongoing will also be presented

For subjects who fail screening, the reasons for screen failure including details on which inclusion/exclusion criteria were not met will be summarized and listed.

For the enrolled population, the number and percentage of participants in each analysis population will be presented. Inclusion/exclusion in each study population will also be listed, together with reasons for exclusion.

The number and percentage of participants with data available for each study day, broken down by inpatient or outpatient status will be summarized.

8.2 Protocol Deviations

The number and percentage of participants in the ITT population with at least one major protocol deviation will be summarized by treatment group and overall, together with the number and percentage of participants reporting at least one major protocol deviation within each category.

All protocol deviations will also be listed.

8.3 Demographic and Baseline Variables

All summaries of demographic and baseline variables will be presented by treatment group and overall using the ITT population.

The following summaries will be produced, using appropriate summary statistics as specified in [Section 8](#):

- Demographic variables: age, sex, race, ethnicity, height weight and BMI
- Smoking status (never, former, current), type of smoking product used, years since last smoked and pack-years.
- Baseline disease characteristics: time since start of symptoms, time since first positive RTPCR test, SpO₂, S/F ratio, WHO OSCI score and temperature

8.4 Concurrent Illnesses and Medical Conditions

All summaries of concurrent illnesses and medical conditions will be presented by treatment group and overall using the ITT population.

Concurrent illnesses and medical conditions will be classified as 'current' if the end date is on or after the date of first dose of study drug, or the condition has been marked as ongoing. Otherwise they will be classified as 'past'.

Targeted questions will be used to report the following known comorbidities for COVID-19 as part of the medical history CRF page:

- Type 1 diabetes
- Type 2 diabetes
- Hypertension
- Other chronic cardiovascular disease
- Chronic respiratory disease
- Ongoing diagnosis of cancer

In addition, other medical history and concurrent illnesses will be captured and coded using the v23.0 of the Medical Dictionary for Regulatory Activities (MedDRA®).

The number and percentage of participants reporting each relevant medical condition will be summarized together with the following potential risk factors for severe illness with COVID-19 which will be assessed from the demographic and baseline data:

- Age ≥ 60 years
- Male
- Non-white or Hispanic/Latino
- Obesity (BMI ≥ 30 kg/m²)
- Current smoker
- Baseline WHO OSCI score of 5
- Baseline neutrophils $> 8.0 \times 10^3/\mu\text{L}$
- Baseline CRP $> 40 \text{ mg/dL}$

In addition, the number and percentage of participants reporting 0, 1, 2, 3, 4, ≥ 5 potential risk factors will be summarized.

All medical history will be summarized, individually for past and current conditions. All medical history will be listed.

8.5 Prior and Concomitant Therapy

Medications will be coded according to the World Health Organization Drug Dictionary (WHODD) Version dated 01Mar2020. Medical procedures will not be coded.

Oxygen therapy will be collected on a separate CRF page and will be considered part of the efficacy data with the reporting described in [Section 9.3.6](#).

Concomitant medications are defined as any medications taken during the treatment period or follow-up period after treatment. This includes any medications started before the first dose and ongoing after the first dose. Prior medications are defined as any medication taken before or during the screening period which were stopped before the first dose of study medication.

Missing and partial start and stop dates will be imputed using the rules specified in [Section 7.3.2](#) before classifying therapies as prior or concomitant. If the classification is still ambiguous after missing and partial dates have been imputed, then the medication will be considered concomitant.

Medications will be summarized using the ITT population, by treatment group and overall and the WHODD Anatomical Main Group (Level 1), Therapeutic Subgroup (Level 2) and preferred term. The summaries will report incidence within each relevant level so that a participant taking multiple medications coded to the same relevant Level 1, Level 2 or preferred term would only be counted once within the incidence count for that level or term.

Concomitant medications taken for COVID-19 will be defined using the indication field on the CRF.

Separate summaries will be produced for each of the following:

- Prior medications
- Concomitant medications taken for COVID-19
- Concomitant medications taken for COVID-19 started pre-treatment
- Concomitant medications taken for COVID-19 during the treatment period (including any which started pre-treatment)
- Concomitant medications taken for COVID-19 started during the follow-up period
- Concomitant medications not taken for COVID-19
- Concomitant medications not taken for COVID-19 started pre-treatment
- Concomitant medications not taken for COVID-19 during the treatment period (including any which started pre-treatment)
- Concomitant medications not taken for COVID-19 started during the follow-up period

All prior and concomitant medications will be listed. Concomitant medical procedures carried out during the study will be listed separately.

8.6 Compliance

Treatment compliance will be summarized for the safety population and daily diary compliance will be summarized for the ITT population, by treatment group and overall.

Treatment and daily diary compliance data will also be listed.

9 Efficacy Analyses

Unless otherwise specified, all efficacy summaries and analyses will be presented by treatment group and overall. The ITT population will be used for all summaries and analyses of efficacy.

In addition to the inferential analyses described below, descriptive statistics will be provided to summarize all efficacy endpoints by treatment group.

For categorical variables, summary tabulations of frequency and percentage of participants within each category will be presented.

For continuous variables, the number of participants, mean, median, standard deviation (SD), minimum, and maximum values will be presented.

For time to event endpoints, the number of participants with the event, the number of participants censored will be presented together with Kaplan-Meier estimates of median time to event and the predicted proportion of subjects with the event at Days 4, 7, 14, 21 and 42 as appropriate to the endpoint. Kaplan-Meier curves of time to event will also be presented.

All analyses will be considered as descriptive only and no adjustment for multiple testing will be performed.

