5.3.3.5 Overall Survival and Intubation and Mechanical Ventilation Free Survival

Overall survival (OS) is defined as the time in days from randomization until death by any cause.

Intubation and mechanical ventilation free survival (IMVFS) is defined as the time in days from randomization until the earliest event of death by any cause or requirement for intubation and/or mechanical ventilation as indicated by the first occurrence of a WHO OSCI score of 6 or above.

Participants who complete the 42-day study period or prematurely withdraw from the study without experiencing the relevant event will be censored on the date of study completion/withdrawal.

Participants who prematurely withdraw from treatment but remain in the study will not be censored and will continue to be followed up until the first occurrence of the relevant event, study completion or withdrawal from the study.

Time to the relevant event will be calculated as:

$$\text{Time to event (days)} = \text{Date of event/censoring} - \text{date of randomization} + 1$$

5.3.3.6 Time to Discharge, Time to SpO2 ≥94% on Room Air and Time to Recovery

Time to discharge is defined as the time in days from randomization until the date of discharge.

Time to SpO2 ≥94% on room air is defined as the time in days from randomization to the first day at which an SpO2 measurement ≥94% on room air is reported after which there were no further requirements for oxygen therapy during the study.

Time to recovery is defined as the time in days from the date of symptom onset until the first day on which a WHO OSCI score of 0 is reported with no further increase above 0 during the study.

Participants who die during the study before the relevant event occurring will be given a status of 'death' which will be considered as a competing risk rather than an event or a censored observation in the analysis.

Participants who are still alive at the end of the 42-day study period or who withdraw prematurely from the study for reasons other than death without experiencing the relevant event will be censored on the date of study completion/withdrawal.

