9.3.5.1 Estimands

The endpoint will be time to event in days as defined in [Section 5.3.3.6](#). The population summary measure of interest will be the hazard ratio for the EDP1815 group compared to the placebo group.

The intercurrent event strategy for these estimands is described in [Table 13](#).

Table 13 Intercurrent Event Strategies for Time to Discharge, Time to SpO₂ ≥94% on Room Air and Time to Recovery Secondary Estimands

Intercurrent event	Strategy to account for intercurrent event		
	Time to Discharge	Time to SpO ₂ ≥94% on Room Air	Time to Recovery
Death prior to the event	Competing Event Death will be considered as a competing event and accounted for as such in the analysis		
Discharge prior to the event with oxygen for home use	N/A	While-on-treatment Participant will be censored on the date of discharge	Treatment policy Actual values will be used regardless of inpatient/outpatient status
Discharged prior to the event without oxygen for home use	N/A	Composite Participant will be considered as having had the event on the date of discharge	Treatment policy Actual values will be used regardless of inpatient/outpatient status
Treatment discontinuation before the study day of interest without withdrawal from the study	Treatment policy Actual values will be used regardless of inpatient/outpatient status		
Withdrawal from the study for any reason	While-on-treatment Participant will be censored on the date of study withdrawal		

For the interim analysis presented at the DMC meeting when 60 patients have completed 21 days in the study, subjects who are still ongoing and have not met the criteria for the relevant event will be censored at the date of the data cut.

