9.3.5.2 Analytical Approach

Time to discharge will be analyzed using a Fine and Gray subdistributional hazards model to allow for the competing risk of death (Fine, 1999). The model will include a parameter for treatment together with any additional baseline covariates identified during the blinded review of the time to discharge model.

The number and percentage of participants who are discharged, who die and who are censored will be reported together the estimate of median time to the event, and the predicted proportion of participants who were discharged at Days 4, 7, 14, 21 and 42. The estimated subdistributional hazard ratio (with 95% confidence interval) for treatment difference in risk of recovery and its p-value from the model will also be presented. Cumulative incidence functions for time to full recovery will also be plotted by treatment group.

Time to discharge information will be listed including event status and time to event/censoring or death.

Time to SpO₂ ≥94% on room and time to recovery will be analyzed in the same manner as described above for time to discharge.

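### The general Kaplan-Meier rule for time-to-event summaries conflicts with treating death as a competing risk for discharge, SpO2 ≥94% and recovery, and SAP 9.3.5.2 names no estimator to settle it

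*SAP*

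**What the plan says.** The general descriptive rule is in the opening text of SAP section 9 and, in the same terms, in Protocol 9.4. For time-to-event endpoints it asks for counts of events and of censored observations, and for "Kaplan-Meier estimates of median time to event and the predicted proportion of subjects with the event". These proportions are to be shown "at Days 4, 7, 14, 21 and 42 as appropriate to the endpoint". A further sentence states that "Kaplan-Meier curves of time to event will also be presented". No endpoint is exempted by name.

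The endpoint-specific text for discharge, SpO2 ≥94% on room air and recovery differs:

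- SAP 5.3.3.6: a participant who dies before the event has a status that "will be considered as a competing risk rather than an event or a censored observation in the analysis".
- SAP Table 13 (9.3.5.1): "Death will be considered as a competing event and accounted for as such in the analysis". Protocol Table 7 takes the same line for these endpoints.
- SAP 9.3.5.2: "Time to discharge will be analyzed using a Fine and Gray subdistributional hazards model to allow for the competing risk of death". On the summary table, it says that those "who are discharged, who die and who are censored will be reported together the estimate of median time to the event". It also asks for "the predicted proportion of participants who were discharged at Days 4, 7, 14, 21 and 42". The other two endpoints follow the same method. No estimator is named for the median or the proportions.
- SAP 16.2.2: cumulative incidence functions for these three endpoints (Figures 14.2.7 to 14.2.9), and Kaplan-Meier curves only for overall survival and intubation and mechanical ventilation free survival (Figures 14.2.5 and 14.2.6).

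**The concern.** Standard Kaplan-Meier recognises two states, event and censored. Applied to time to discharge, it normally censors a death on its date. The estimate then treats those who died as if they could still be discharged later at the same rate as those remaining in hospital. SAP 5.3.3.6 rules this out, yet the only estimator the plan names for medians and day-specific proportions is Kaplan-Meier. A programmer following section 9 literally would fill Tables 14.2.7 to 14.2.9 with figures that disagree with the cumulative incidence figures of the same number.

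Two settings make this matter. Tables and figures both go to the DMC at the 60-participant meeting, where extension by 40 is considered. And if the study stops early for low recruitment, SAP 9.1.1.1 drops figures and inferential efficacy analyses, so these tabulated summaries would stand without the curves that would expose a discrepancy.

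**Working it through.** **The plan's own figures.** The plan states no expected rate for discharge, SpO2 ≥94%, recovery or death. Its only design figures are the confidence interval half-widths in SAP Table 8. They reproduce (60 participants, SD 100: t(0.975, 58) × 100 × √(4/60) = 51.68, stated 51.7) but have no bearing here.

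**Which text governs.** SAP 9.3.4.2 (overall survival) and 9.3.5.2 (discharge) both ask for a median and predicted proportions on the same five days. The first names Kaplan-Meier; the second names nothing. Protocol 9.4.1.2 asks for neither quantity for discharge, so in the protocol their only source is the Kaplan-Meier sentence in 9.4.

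**Size if deaths are censored.** All rates below are assumptions. With constant hazards λ for discharge and m for death:

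- 1 − KM(t) = 1 − exp(−λt)
- cumulative incidence CIF(t) = λ/(λ+m) × [1 − exp(−(λ+m)t)]

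*Set A: λ = 0.10 per day.* Day 42 deaths are (m/λ) × CIF(42): 0.05 × 94.1% = 4.7% for m = 0.005, and 0.20 × 82.8% = 16.6% for m = 0.02.

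| Day | 1 − KM | CIF, m = 0.005 | CIF, m = 0.02 | Overstatement (points) |
|---|---|---|---|---|
| 14 | 75.3% | 73.3% | 67.8% | 2.0 to 7.5 |
| 21 | 87.8% | 84.7% | 76.6% | 3.0 to 11.1 |
| 42 | 98.5% | 94.1% | 82.8% | 4.4 to 15.7 |

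Day 42, m = 0.02: 1 − exp(−4.2) = 0.985 against (0.10/0.12) × [1 − exp(−5.04)] = 0.828.

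*Set B: rates fixed by Day 42 outcomes.* With proportion e discharged and d dead by Day 42, λ+m = −ln(1−e−d)/42 and λ = (λ+m) × e/(e+d). Hence 1 − KM(42) = 1 − (1−e−d)^(e/(e+d)). For e = 80% and d = 10%, this is 1 − 0.10^0.889 = 0.871.

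| Discharged (true) | Dead | 1 − KM at Day 42 | Overstatement (points) |
|---|---|---|---|
| 80% | 2% | 81.2% | 1.2 |
| 80% | 5% | 83.2% | 3.2 |
| 80% | 10% | 87.1% | 7.1 |
| 80% | 15% | 92.0% | 12.0 |
| 70% | 20% | 83.3% | 13.3 |

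Across set B the Day 14 gap is 0.2 to 3.7 points, and the Kaplan-Meier median is 0.2 to 2.5 days too short. With no deaths the two estimators coincide.

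**Between arms.** Take the same λ = 0.10 in both arms and 4.7% against 16.6% deaths. Kaplan-Meier gives 98.5% discharged in each arm, whereas cumulative incidence gives 94.1% and 82.8%, an 11-point difference.

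**Dependence on how deaths are coded.** Take 30 constructed patients: 25 discharged, 3 dead, 2 still in hospital at Day 42. Kaplan-Meier with deaths censored gives 91.4% at Day 42. Aalen-Johansen gives 25/30 = 83.3%. Keeping the deaths in the risk set to the end also gives 83.3%. That equality needs no earlier censoring, and no section of the plan prescribes this coding.

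**The case against.** The strongest reply is that the opening of section 9 is generic and yields to the endpoint-specific text. That text reports three outcomes in place of two, drops the words Kaplan-Meier that the survival section uses, fits a Fine and Gray model and plots cumulative incidence. The general sentence on curves is already overridden for exactly these endpoints by the figure list. The phrase about appropriateness to the endpoint could also be read as an exemption. Much of this stands: competing-risk methods were evidently intended. But that phrase follows the list of days and most naturally limits which days are shown. Nothing in the specific text says how the medians and proportions in the tables are computed.

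A reader might go further and infer two things the documents do not support. The first is that the reported proportions will be too high. That follows only if the general rule is applied with deaths censored, which SAP 5.3.3.6 forbids. The second is that mortality differences would be hidden. The same summary gives the number and percentage who die, efficacy summaries are by treatment group, overall survival has its own table, Cox model and curve, and death is carried forward as WHO OSCI score 8. What could be lost is the effect of mortality on the tabulated discharge and recovery proportions, not the deaths themselves.

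It is also fair that the larger gaps need mortality the plan does not predict. Patients in ICU, ventilated or moribund at screening are excluded, and entry is limited to ages 18 to 65 unless the DMC opens it to older patients.

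**Conclusion.** The inconsistency is real and its severity is minor. The stated rule conflicts with the status the plan gives to death, and SAP 9.3.5.2 leaves the estimator open. Followed literally with deaths censored, the rule overstates the Day 42 proportions by roughly 1 to 16 points for assumed mortality of 2% to 20%, by less on earlier days, and shortens the medians. These sizes rest on constant hazards, with either an assumed discharge hazard of 0.10 per day or an assumed 70% to 80% discharged by Day 42. The main comparison is unaffected, because it is already a Fine and Gray model, and every analysis is declared descriptive. The study is meant to inform later sample sizes, but the documents do not say that these particular proportions will be used for that.

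**What to change.** 1. In the opening text of SAP section 9 and in Protocol 9.4, restrict Kaplan-Meier medians, proportions and curves to overall survival and to intubation and mechanical ventilation free survival. In both of these, death is itself an event (SAP 5.3.3.5).
2. In SAP 9.3.5.2, state that for time to discharge, SpO2 ≥94% on room air and recovery the day-specific proportions come from the Aalen-Johansen cumulative incidence function with death as the competing event. Define the median as the first day on which that function reaches 50%, reported as not reached if it does not.

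The cost is two or three sentences. The cumulative incidence functions are already planned for Figures 14.2.7 to 14.2.9, so the tables can be filled from the same estimates and will then agree with the figures. No new data or models are needed.
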